| Criteria for Evaluation | 
Safety
 
Safety endpoints will include the incidence of adverse events (AEs), SAEs, and infusion-associated reactions (IARs); changes from Baseline in 12-lead electrocardiograms (ECGs) and clinical laboratory tests (hematology, serum chemistry [including lipid panel], and urinalysis); changes in vital signs during and after infusion, relative to pre-infusion values; physical examination findings; use of concomitant medications/therapies; characterization of anti-drug antibodies (ADAs) including ADA titer by time point, peak ADA titer, and time to peak ADA titer. The effect of ADAs on the safety of sebelipase alfa will also be explored, in particular, the relationship between ADA-positive subjects and the incidence of IARs. Functional and overall development in subjects ≤ 6 years of age will be assessed, as determined by Denver II scores.
 
Efficacy
 
Secondary outcome measures include the following changes or percent change from Baseline to the end of the treatment period: (1) decrease in Alanine Aminotransferase (ALT); (2) decrease in Aspartate Aminotransferase (AST); (3) decrease in LDL-C; (4) decrease in non-HDL-C; (5) increase in HDL-C; (6) decrease in TG, (7) decrease in Child-Pugh status, (8) decrease in United Kingdom Model for End-Stage Liver Disease (UK-ELD) score. In the subset of subjects for whom these assessments are performed: (9) improvement in hepatic histology; (10) decrease in liver and spleen volume by magnetic resonance imaging (MRI); and (11) decrease in liver fat fraction by MRI. The effect of sebelipase alfa on growth parameters in pediatric subjects with manifestations of impaired growth will be measured.
 |

| | |
|--------------------------------|--|
| Title | A MULTICENTER, OPEN-LABEL STUDY OF SEBELIPASE ALFA IN PATIENTS WITH LYSOSOMAL ACID LIPASE DEFICIENCY |
| Protocol Number | LAL-CL06 |

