3.2.1. Outcome Variable Selection

3.2.1.1. Safety

The study is designed to primarily evaluate the safety of intravenous (IV) infusions of sebelipase alfa. Outcome variables selected to characterize the safety profile of sebelipase alfa in subjects with LAL Deficiency include:

- The incidence of AEs, SAEs, and IARs;
- Changes from Baseline in 12-lead electrocardiograms (ECGs), and clinical laboratory tests (hematology, serum chemistry [including lipid panel], urinalysis);
- Changes in vital signs during and after infusion, relative to pre-infusion values;

- Physical examination findings;
- Use of concomitant medications/therapies;
- Characterization of ADAs, including ADA titer by time point, peak ADA titer, and time to peak ADA titer;
- Functional and overall development in subjects ≤ 6 years of age, as determined by Denver-II scores.
- Given the potential for ADAs to impact the safety profile of a biological product, the effect of ADAs on the safety of sebelipase alfa will also be explored, in particular, the relationship between ADA-positive subjects and the incidence of IARs.

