| Macrophage Activation Markers | serum chitotriosidase, serum ferritin, hs-CRP, CK-18 |
| Urinalysis ¹ | pH, clarity, color, specific gravity, glucose, ketones, blood, protein, nitrite, and leukocytes (microscopic examination will only be done if urinalysis is positive for blood, nitrite, or leukocytes, or if protein is >1+) |
| Viral Hepatitis Screen | HBsAg and HCV serology |
| Alcohol Use | CDT |
| Coagulation Parameters ¹ | PT (INR), aPTT |
| Pregnancy ² | Serum hCG at Screening and urine hCG ¹ at all other visits |
| Anti-drug Antibody | Anti-sebelipase alfa antibody |
| Exploratory Biomarkers | See Section 5.9.5 . |
| LAL Enzyme Activity | Dried blood spot. See Section 5.9.6 . |
| DNA Sample | See Section 5.9.7 |
| PK Samples | See Section 5.9.4 |
| Malnutrition Markers and Fat Soluble Vitamins | See Laboratory Manual for details |

¹ Test performed by a local laboratory.

² Performed for female subjects of childbearing potential only. In the event of a positive pregnancy test result, refer to [Section 7.2.3](#) for information on pregnancy reporting and follow-up.

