8.7.2. Clinical Laboratory Tests

Observed measurements and changes from Baseline to each study time point in clinical laboratory data will be summarized. Clinically significant abnormal values will be indicated in the listings of laboratory data, and frequencies of abnormal values relative to the laboratory normal range and clinically significant abnormal values will be summarized, if sufficient data are available for analysis.

Immunogenicity data will be summarized, including the number and percentage of subjects who become ADA-positive, time to peak titer, ADA titer by time point, and median and peak ADA titer. Other exploratory analyses of the effect of ADAs on the safety of sebelipase alfa may also be performed as suggested by the type and amount of data available.

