4.1. Changes from Analyses Specified in the Protocol

The following items are specified in the protocol and are not part of this analysis plan:

- The urinalysis summary of the change from baseline will not be summarized. However urinalysis results will be provided in the subject listings.
- The summary of the change in vital signs during and after infusion relative to pre-infusion values will not be summarized; instead, the change from baseline (defined below) to each post-baseline visit will be summarized. Given that multiple vital sign measurements are taken at each post-baseline visit, the average of the measurements within a visit will be summarized.
- At the time of this Statistical Analysis Plan (SAP) amendment, only 2 subjects have been anti-drug antibody (ADA) positive. As a result, a clarification was added that many of the ADA analyses will only be performed in the event that at least 5 subjects are ADA positive.
- The effect of sebelipase alpha on growth parameters in pediatric subjects will be evaluated among all subjects younger than 18 years old. The protocol specifies analyzing these data conditional on subjects having had manifestations of impaired growth. However, the analysis will not be limited to subjects showing signs of impaired growth.
- The AE table showing the incidence of AEs across time intervals will not be presented.
- The protocol indicates that percentages will be calculated including subjects with missing values.
 However, percentages will be based on subjects with non-missing values unless otherwise specified.

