4.2. Changes from Analyses Specified in the Previous Version of the SAP

In addition to items described in Section 4.1, Changes from Analyses Specified in the Protocol, the additions, clarifications and a few deletions have been made to the previous version of the SAP.

The following additional summaries have been described in this version of the SAP:

- Additional baseline characteristics are summarized including, among others, a summary of the LAL enzyme activity and DNA results at baseline.
- The number and percentage of subjects on a modified diet at baseline and with changes in diet over the course of the treatment period are summarized.
- The number of weeks on specific doses of sebelipase alpha is summarized.
- A listing of infusion associated reactions (IARs) for those subjects with a change in sebelipase alpha dosing is added.
- Summaries of select laboratory parameters will be presented relative to the upper limit of normal (ULN).
- The summary of the Child-Pugh Status is described.
- Details of the physical examination summaries are provided.
- A shift from baseline in the interpretation of the 12-lead ECGs has been described.
- The percent change from baseline is added as a summary of each endpoint for which a change from baseline was planned.
- The United Kingdom Model for End-Stage Liver Disease (UK-MELD) summary is described.
- A summary of the post-baseline LAL enzyme activity is described.

The following clarifications have been provided to this version of the SAP:

- Medical histories are summarized separately for those identified as prior and concomitant disease.
- The Denver II assessment will be presented using the overall score and not the domain scores.
- Exploratory analyses of the effect of ADAs on the efficacy of SBC-102 will not be explored using stratified analyses. This may be added if at least 5 subjects are ADA positive at the time of the analysis.
- Laboratory abnormalities will not be specified as CS (Clinically Significant) or NCS (Not-Clinically Significant) by the Investigator or designee; instead, clinically significant changes from a subject's baseline value or previous values are recorded as AEs.

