5.1. Safety

5.1.1. Primary Endpoint(s)

This study is designed primarily to evaluate the safety of IV infusion of SBC-102. Safety will be assessed based on: incidence and severity of TEAEs, serious adverse events (SAEs), and IARs; changes from baseline through trial completion in vital signs, Electrocardiogram (ECG), and routine clinical laboratory tests (chemistry, hematology, urinalysis); physical examination findings; use of concomitant medications/treatments; functional and overall development measured using the Denver II Development Screening Test; and incidence/titer of antibodies to SBC-102.

5.1.1.1. Adverse Events (AEs), Serious Adverse Events (SAEs) and Infusion-Associated Reactions (IARs)

See Section 7.1 of study protocol for definitions.

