7.2.3. Laboratory Tests

Observed measurements and changes from Baseline to each study time point in clinical laboratory data will be summarized. Frequencies of results relative to the laboratory normal range as well as shift tables showing the change from baseline to post-baseline relative to the normal range will be summarized, if sufficient data are available for analysis. Summaries will be presented for liver function tests, serum lipids, hematology, serum chemistry, HbA1c, and coagulation parameters as identified in Table 2, Clinical Laboratory Tests, above.

Plots of mean observed values, absolute change from baseline and mean percent change from baseline over time with standard error bars may be prepared for the following:

- Liver function tests: ALT/AST, GGT, total bilirubin, direct bilirubin, indirect bilirubin, albumin, alkaline phosphatase
- Lipids: total cholesterol, LDL-C, non-HDL-C, HDL-C, triglycerides
- Hematology: hemoglobin, platelets

Also see Section 7.3.2 Clinical Laboratory Tests as described in the Efficacy Analyses section.

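### Urinalysis change is a named safety endpoint, but the SAP plans no urinalysis table, so new urine protein or blood not reported as an adverse event is only listed

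*Protocol*

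**What the plan says.** **Endpoint.** Protocol 3.2.1.1 states: "The study is designed to primarily evaluate the safety of intravenous (IV) infusions of sebelipase alfa". That section and the synopsis both list change from Baseline in urinalysis among the safety outcomes; the synopsis wording is "clinical laboratory tests (hematology, serum chemistry [including lipid panel], and urinalysis". SAP 5.1.1, the section for primary endpoints, repeats it: "routine clinical laboratory tests (chemistry, hematology, urinalysis".

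**Data collected.** Protocol Table 1 gives the urinalysis items as "pH, clarity, color, specific gravity, glucose, ketones, blood, protein, nitrite, and leukocytes". Appendix B schedules urinalysis at Screening and every 12 weeks from Week 12, for adults and children alike. The test is run by local laboratories.

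**Protocol analysis.** Protocol 8.7.2 makes no exception for urinalysis: "Observed measurements and changes from Baseline to each study time point in clinical laboratory data will be summarized". It adds frequencies of abnormal and clinically significant values, on condition that there are enough data.

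**SAP analysis.** SAP 4.1, which declares departures from the protocol, says "The urinalysis summary of the change from baseline will not be summarized" and keeps the results in listings. SAP 7.2.3 covers change summaries, frequencies against the normal range and shift tables, and then names the panels: "Summaries will be presented for liver function tests, serum lipids, hematology, serum chemistry, HbA1c, and coagulation parameters as identified in Table 2". Urinalysis is not among them.

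**The concern.** Safety is the primary objective, and the study is descriptive, so its tables are its output. Here a named safety endpoint has no planned summary, and the section that withdraws the summary gives no reason. The SAP therefore disagrees with itself: 5.1.1 lists urinalysis as an endpoint, SAP 7 promises tables or graphs for each endpoint as suits the data, and 4.1 with 7.2.3 provide none.

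At stake is whether the report can say how many subjects with a baseline and a later urine result developed protein or blood in the urine, or that none did. A listing holds the raw results but leaves that count to the reader.

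**Working it through.** The plan gives no figure to reproduce. The check compares the texts, and one calculation shows what a table would add.

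**1. Is urinalysis still an endpoint in the current SAP?** Yes, in 5.1.1.

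**2. Does any SAP section plan a urinalysis table?** No. Section 4.1 withdraws the change summary, and the panel list in 7.2.3 omits urinalysis. The efficacy laboratory section (7.3.2) covers liver tests, lipids, hemoglobin, platelets and the liver disease score.

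**3. Do the documents supply a reason?** None is stated, and the obvious candidates do not fit the rest of the SAP:
- *Categorical results.* ECG (7.2.7), Denver II (7.2.8) and Child-Pugh class (7.2.4) are categorical, and each gets a shift table.
- *Local testing.* Coagulation is also run locally (Table 2 footnote), and 7.2.3 summarizes it.
- *Replacement by another summary.* When 4.1 drops the vital-sign summary around infusions, it puts another summary in its place. Urinalysis gets listings only.

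**4. What reaches a table by another route?** Protocol 5.9.3 and 7.1.2 and SAP 5.1.1.4 have clinically significant laboratory changes recorded as adverse events. SAP 7.2.2.2 tabulates treatment-emergent events by system organ class and preferred term, with severity and causality. Protocol 7.1.2 also tells sites not to report out-of-range values as adverse events unless they judge the change clinically significant. So the route depends on investigator judgement, and its percentages use the analysis population, or treated subjects (SAP 7.2.2.2 and 9.4.7.1), not subjects with a baseline and a later urine result. A urine finding missing from the adverse event table is not a recorded zero.

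**5. How informative are the listings?** Protocol 8.7.2 would flag clinically significant values there. SAP 4.2 says "Laboratory abnormalities will not be specified as CS (Clinically Significant) or NCS (Not-Clinically Significant) by the Investigator or designee", and the same sentence sends significant changes to adverse event reporting instead. The judgement is kept, but the laboratory listing no longer shows it.

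**6. What would a tabulated zero be worth?** SAP 7 specifies the Clopper-Pearson interval. For 0 events in n subjects the two-sided 95% upper limit is 1 − 0.025^(1/n).
- n = 30 (Protocol 8.2, approximate): 1 − 0.025^(1/30) = 1 − 0.884 = 11.6%.
- n = 20 (SAP 9.3, not expected to be exceeded): 1 − 0.025^(1/20) = 1 − 0.832 = 16.8%.

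Both assume that every subject has a baseline and a later urine result; with fewer evaluated, the limit is higher.

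**The case against.** The strongest defence has four parts.

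- **Clinically important findings are not lost.** They become adverse events and are tabulated. This stands. A reader might infer from SAP 4.1 and 7.2.3 that new proteinuria or haematuria will appear in no table at all. The documents do not support that: a change the investigator judges clinically significant reaches the adverse event tables, and every result is listed.
- **The departure is declared.** This also stands. SAP 4.1 is the right place for it and says what replaces the summary. What is missing is the reason and agreement with 5.1.1.
- **The protocol did not promise a urinalysis shift table.** Correct. The synopsis says only that shift tables may be built for some parameters, Protocol 8.7.2 makes abnormality frequencies conditional on enough data, and SAP 7 asks for tables that suit the data. A mean change is a poor summary of dipstick grades, so dropping it is defensible. That argues for a categorical table, as the SAP uses for other categorical safety measures, rather than for none.
- **The study is small, single-arm and descriptive.** True, and it limits the severity. No test or estimate changes.

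Nothing in the documents points to a renal signal, and SAP 4.1 notes only 2 antibody-positive subjects when it was amended. The point rests on the endpoint having been named, not on an expected harm.

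**Conclusion.** The concern holds in a limited form. The SAP names change in urinalysis as a safety endpoint and plans no summary of it, without a reason. New urine protein or blood not reported as an adverse event will be visible only in listings, with no number evaluated and no number affected.

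The loss is modest: one safety statement that the plan as written cannot make. If no subject had a new abnormality, it would carry an exact 95% upper limit of 11.6% for 30 subjects or 16.8% for 20. The documents give no expected incidence of urine abnormalities, so the number of findings that would go untabulated cannot be estimated. The change should be made because the data are already collected and the table is cheap; it does not threaten the study's conclusions.

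**What to change.** **SAP 7.2.3.** Add a categorical shift table from Baseline to the worst post-baseline result for urine protein and for blood. Protein could use negative or trace, 1+, and above 1+; above 1+ is already the protocol's trigger for microscopy. Report the number of subjects with a baseline and a later result, the number and percentage with a new abnormal result, and the exact 95% interval from SAP 7. State whether unscheduled results count toward the worst value, since SAP 7 otherwise sends them to listings. State also which pre-dose result is Baseline if there are several, because the averaging rule in SAP 9.4.5.1 does not suit grades.

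**SAP 4.1.** Revise the urinalysis bullet and keep it: the remaining items are listed only, and the reason is given.

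**SAP 5.1.1.** Align the endpoint wording with what will be summarized.

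**Cost.** One extra table from data in hand, plus a mapping of local-laboratory grades to common categories.

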Table 2 PK Sampling in Pediatric Subjects (Age < 18 Years at Informed Consent).....49
Table 3 PK Sampling in Select Adult Subjects (Age ≥ 18 Years at Informed Consent).....50
Table 4 Health-Related Quality of Life Assessments54
Table 5 Assessment of Causality61
Table 6 Management of Infusion-Associated Reactions63

List of Figures

Figure 1 Study Flow Diagram30
Figure 2 Dosing Flow Diagram57

List of Abbreviations

| | |
|------------------|--|
| ADA | Anti-drug Antibody |
| AE | Adverse Event |
| ALT | Alanine Aminotransferase |
| aPTT | Activated Partial Thromboplastin Time |
| AST | Aspartate Aminotransferase |
| AUC | Area Under the Serum Concentration Time Curve |
| AUDIT | Alcohol Use Disorder Identification Test |
| BMI | Body Mass Index |
| CDC | Centers for Disease Control and Prevention |
| CDT | Carbohydrate-Deficient Transferrin |
| CLDQ | Chronic Liver Disease Questionnaire |
| C _{max} | Maximum Observed Concentration |
| CS | Clinically Significant |
| CSR | Clinical Study Report |
| CTCAE | Common Terminology Criteria for Adverse Events |
| DBS | Dried Blood Spot |
| DNA | Deoxyribonucleic acid |
| EGD | Esophagogastroduodenoscopy |
| ECG | Electrocardiogram |
| eCRF | Electronic Case Report Form |
| ERT | Enzyme Replacement Therapy |
| FACIT-Fatigue | Functional Assessment of Chronic Illness Therapy-Fatigue |
| FDA | Food and Drug Administration |
| GCP | Good Clinical Practice |
| GGT | Gamma-Glutamyl Transferase |
| GlcNAc | N-acetylglucosamine |
| HbA1c | Glycosylated Hemoglobin |
| hCG | Human Chorionic Gonadotropin |
| HDL-C | High-Density Lipoprotein Cholesterol |
| HRQOL | Health-Related Quality of Life |
| hs-CRP | High-Sensitivity C-Reactive Protein |
| HVPG | Hepatic Venous Pressure Gradient |
| IAR | Infusion-Associate Reaction |
| IB | Investigator Brochure |
| ICH | International Conference on Harmonisation |
| IEC | Independent Ethics Committee |
| IMP | Investigational Medicinal Product |
| IND | Investigational New Drug |
| IRB | Institutional Review Board |
| IV | Intravenous |
| LAL | Lysosomal Acid Lipase |
| LAL Deficiency | Lysosomal Acid Lipase Deficiency |
| LDL-C | Low-Density Lipoprotein Cholesterol |
| LLOQ | Lower Limit of Quantification |
| LSD | Lysosomal Storage Disorder |
| M6P | Mannose-6-phosphate |
| MCV | Mean Corpuscular Volume |

| | |
|-----------|---|
| MCH(C) | Mean Corpuscular Hemoglobin (Concentration) |
| MMR | Macrophage Mannose Receptor |
| MRI | Magnetic Resonance Imaging |
| NCS | Not Clinically Significant |
| PD | Pharmacodynamics |
| PedsQL | Pediatric Quality of Life Inventory |
| PK | Pharmacokinetic(s) |
| PT (INR) | Prothrombin Time (International Normalized Ratio) |
| qw | Once Weekly |
| qow | Every Other Week |
| rhLAL | Recombinant Human Lysosomal Acid Lipase |
| SAE | Serious Adverse Event/Serious Adverse Experience |
| SAP | Statistical Analysis Plan |
| SC | Safety Committee |
| SOM | Study Operations Manual |
| $t_{1/2}$ | Terminal Elimination Half-Life |
| TG | Triglyceride(s) |
| TEAE | Treatment-Emergent Adverse Event |
| T_{max} | Time to Maximum Observed Concentration |
| UDCA | Ursodeoxycholic Acid |
| UK-ELD | United Kingdom Model for End-Stage Liver Disease |
| US | United States |
| WFA | Weight-for-Age |
| WHO | World Health Organization |

1. Introduction

This document is a protocol for a human research study. This study is to be conducted according to United States (US) and international standards of Good Clinical Practice (GCP) Food and Drug Administration (FDA) Title 21 part 312 and International Conference on Harmonisation (ICH) guidelines), applicable government regulations and institutional research policies and procedures.

1.1. Background

1.1.1. Lysosomal Acid Lipase Deficiency

Lysosomal acid lipase (LAL) deficiency (LAL Deficiency) (Online Mendelian Inheritance in Man database number 278000) is a serious and life-threatening multisystem storage disorder caused by a marked decrease in LAL enzyme activity. LAL plays a key role in the metabolism and degradation of lipids, predominantly cholesteryl esters, and triglycerides, and its marked reduction or absence in patients with LAL Deficiency leads to accumulation of these lipids in various tissues and cell types throughout the body. There are no safe or effective therapies for LAL Deficiency.

LAL Deficiency is caused by mutations affecting the *LIPA* gene located on chromosome 10q23.2-q23.3. The most rapidly progressive form of LAL Deficiency presents in infants and is associated with a variety of private mutations that likely result in a complete loss of enzyme function ([Grabowski et al., 2012](#)); LAL Deficiency presenting in children and adults is frequently associated with a common exon-8 splice-junction mutation that may result in some residual enzyme activity.

1.1.2. Clinical Presentation of LAL Deficiency

LAL Deficiency is associated with significant ill health and a shortened life expectancy. As is the case for many other lysosomal storage disorders, subjects with LAL Deficiency present and progress as a continuum, with prominent liver pathology, and dyslipidemia.

LAL Deficiency presenting in children and adults, sometimes called cholesteryl ester storage disease, is the most common presentation, and is an underappreciated cause of cirrhosis, dyslipidemia and accelerated atherosclerosis. In the majority of reported cases, subjects are diagnosed before the age of 20. Although disease presentation can be variable, hepatic manifestations typically dominate the clinical picture ([Bernstein et al., 2013](#)). Diagnosis of LAL Deficiency requires a high index of clinical suspicion, since elevated transaminases, fatty liver, and hyperlipidemia (either alone or in combination) are also seen in subjects with other liver and metabolic diseases.

In LAL Deficiency, the presence of increased lysosomal cholesteryl esters and triglycerides in the liver is associated with liver fibrosis and progression to cirrhosis. Published cases clearly demonstrate that progression of fibrosis to cirrhosis or clinical complications of chronic liver disease, including bleeding ascites and esophageal varices, occur across the age spectrum (Bernstein, et al., 2013).

Dyslipidemia with elevated total cholesterol, triglycerides, and low-density lipoprotein-cholesterol (LDL-C) and decreased high-density lipoprotein-cholesterol (HDL-C) levels is common and has been shown to be associated with accelerated atherosclerosis (Beaudet et al., 1977; Anderson et al., 1999; Elleder et al., 2000). Although textbook descriptions describe elevated LDL and triglycerides (TG) in affected cases (Type II hyperlipidemia), recent insights suggest that isolated elevation of LDL may be present in a number of cases (Tripuraneni et al, 2013).

In addition to the more common manifestations of LAL Deficiency, other clinical presentations and complications have been described, including pulmonary hypertension (Cagle et al., 1986), severe hypersplenism and splenic infarcts (Guzzetta et al., 1990), and mesenteric lipodystrophy (vom Dahl et al., 1999). Growth failure, defined as > 2 standard deviations below normal weight and height measurements for age, has been noted in some children and adults with LAL Deficiency. Gastrointestinal involvement occurs in most LAL Deficiency subjects. However, infants with LAL Deficiency typically present with chronic diarrhea, emesis, malabsorption and failure to thrive.

LAL Deficiency presenting in infants, historically called Wolman disease, is a more rare presentation of the disease and is usually fatal within the first 6 months of life. Named after the physician who first described it (Abramov et al., 1956), this is the most aggressive presentation of LAL Deficiency, with growth failure as the predominant clinical feature and a key contributor to the early mortality. Rapidly progressive hepatic disease, as evidenced by liver enlargement, elevation of transaminases, hyperbilirubinemia, coagulopathy, and hypoalbuminemia, also occurs in these infants and contributes to mortality (Anderson et al., 1999; Mayatepek et al., 1999).

At present, there are no therapies approved by regulatory authorities for the treatment of LAL Deficiency. In infants, a variety of supportive therapies are used in an attempt to mitigate some of the effects of this rapidly fatal disease. Although some temporary stabilization of the clinical condition has been described, these interventions are not believed to substantially modify the outcome in affected subjects (Hoeg et al., 1984; Meyers et al., 1985). With few exceptions, success has not been achieved using bone marrow/hematopoietic stem cell transplantation. These methods are frequently limited in use and/or associated with high mortality due to the condition of the subjects at the time of diagnosis. Additionally, bone marrow/hematopoietic stem cell transplantation carries the inherent risks associated with these procedures, including graft-versus-host disease (Krivit et al., 2000; Stein et al., 2007; Tolar et al., 2009; Yanir et al., 2013).

Treatment for children or adults presenting with LAL Deficiency is limited to management of dyslipidemia through diet and the use of lipid-lowering therapies. The impact of lipid-lowering agents such as hydroxymethylglutaryl coenzyme A reductase inhibitors (statins) is limited, since they do not address the root cause of LAL Deficiency, and disease progression to end stage liver failure still occurs (Ginsberg et al., 1987; Di Bisceglie et al., 1990; Tarantino et al., 1991; Yokoyama & McCoy, 1992; Glueck et al., 1992; Gasche et al., 1997; Assmann & Seedorf, 2001; Tadiboyina et al., 2005). As liver function deteriorates, liver transplantation may be required. At present, there is limited information on the long-term outcomes of liver transplantation in subjects with LAL Deficiency (Ferry et al., 1991; Hansen & Horslen, 2008).

